***Modifying the final phase of the study based on findings from interim analyses***

Interim analyses of the pre-Month 6 study data have provided new information related to some of the study’s main research questions and have informed modifications to the final phase of the study. Consistent with observations in HIV-negative populations, mRNA-1273 appears safe and well tolerated in PLWH. Reactions after vaccinations were largely mild, with few severe reactions (3%) and no life-threatening or fatal reactions. To date, adverse events in general have been overwhelmingly mild and only one serious adverse event (a case of angioedema) has been considered potentially related to the vaccine. The pre-Month 6 data also suggest that in our study population, participants with hybrid immunity (ie, immunity from both prior infection and vaccination) experienced a reduced incidence of symptomatic SARS-CoV-2 infections compared to participants with only vaccine-induced immunity. Specifically, PLWH and HIV-negative participants who had evidence of prior SARS-CoV-2 infection at baseline and received one dose of mRNA-1273 had an annual COVID-19 incidence rate of 2.2% and 1.5% respectively, compared to 7.1% and 5.8% among such groups without evidence of prior infection at baseline and received two doses of mRNA-1273. This reduction in SARS-CoV-2 incidence could be due to the combination of natural immunity and mRNA-1273 vaccination or due to natural immunity alone. In addition, serious COVID-19 has been very rare in our study population during the pre-Month 6 period, with only 9 cases identified to date, including 7 in PLWH and 2 in people who were HIV-negative. However, asymptomatic SARS-CoV-2 infections were more common than previously appreciated, representing 86% of pre-Month 6 cases. In addition, the data suggest that there are a significant number of likely persistent infections. Of the 1298 (9.3%) participants with at least

one SARS-CoV-2 positive NAAT, 5.6%, 1.8%, and 1.5% were persistently NAAT positive at  $\geq 25$ , 50, 100 days, respectively. Deep genome sequencing of the sequential samples will help determine if these are persistent infections or reinfections (likely both) and what proportion of infections have acquired mutations. The persistent/recurrent infections appear to be more common among the participants without prior SARS-CoV-2 infection, those with active tuberculosis, and PLWH who have low CD4 T-cell counts and/or HIV viremia.

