the trial, including providing access to temperature monitoring, personal pulse oximetry monitoring, oxygen, medications such as steroids, and hospitalization at facilities that are both prepared and experienced with the management of severe cases to minimize potential complications of COVID-19 disease. Study data collected on the duration of viral shedding, PCR cycle thresholds, and viral sequencing may also contribute to optimizing management of SARS-CoV-2 infected participants. The incidence of breakthrough infections will be carefully monitored throughout the study and if there are concerning relative rates of infections among study groups (eg, high incidence of infections in the hybrid immunity group), the DSMB or OG will make recommendations to adjust the course of the study to protect the safety and wellbeing of participants (eg, it could recommend that the study be modified to include an additional vaccine dose, if appropriate). In addition, as previously mentioned, at the start of Month 6 vaccinations (involving mRNA-1273 versus mRNA-1273.222), there will be a vaccination pause after the approximately first 120 participants are vaccinated (the “Month 6 sentinel cohort”) so that reactogenicity data may be reviewed before a decision is made on whether to continue with these vaccinations.

Specific features not present in most study designs of US Government’s Department of Health and Human Services [HHS] Coordination Operations and Response Element (HCORE) (previously known as Federal COVID-19 Response, Operation Warp Speed [OWS], and Countermeasures Accelerations Group [CAG]) are included in this study to assess vaccine efficacy against severe COVID-19 as a coprimary efficacy objective in addition to assessing vaccine efficacy against symptomatic infection. Severe COVID-19 is included as a coprimary endpoint because: (1) this endpoint is highly clinically significant, (2) it is feasible to power the study for this endpoint given data showing that a sizable percentage of symptomatic infections are severe in trial countries, and (3) the use of coprimary endpoints can improve statistical power (57).

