### 6.3.1 Power calculations for coprimary objectives 1-4 (Efficacy)

Let  $VE(COVID)$  and  $VE(Severe\ COVID)$  denote vaccine efficacy of the vaccine regimen vs. counterfactual placebo among baseline SARS-CoV-2 negative participants against COVID-19 and severe COVID-19, respectively. The relative risk objectives are assessed in terms of cumulative incidence ratios between the active vaccine regimens without analysis of counterfactual placebo arms; the notations  $VE(COVID)$  and  $VE(Severe\ COVID)$  are mainly used for purposes of communicating effect sizes.

The following calculations focus on the COVID-19 endpoint because the severe COVID-19 endpoint could potentially be changed to be a secondary endpoint if there are insufficient severe COVID endpoints (Section 6.4.3). For the assessment of pre-Month 6 stage objectives, sample sizes of Groups 1 and 2 in the FAS are considered. For the assessment of post-Month 6 stage objectives, the following calculations consider approximately 4000 participants in Groups 1-4 received their Month 6 vaccination (mRNA-1273 vs. mRNA-1273.222) per randomization under protocol version 6. This sample size is consistent with study data as of June 2023. As shown in the upper portion (pre-Month 6 stage) of Table 6-2, there is ample power ( $> 90\%$ ) to detect a relative risk of 2.0 between Groups 1 and 2 against the null hypothesis  $H_0: RR = 1.0$  during Month 0 and 6 in the pre-Month 6 stage. In reality, the sample sizes of the PLWH hybrid immunity group who receive 1 pre-Month 6 dose and the PLWH pure vaccine group who receive 2 pre-Month 6 doses are likely smaller than the sample sizes of Groups 1 and 2, respectively. As shown in the lower portion (post-Month 6 stage) of Table 6-2, when the annual incidence of the primary endpoint is in the range of 2.5%- 3.5% in the mRNA-1273 arm, there is approximately 80-90% power to detect a relative risk of 2.0 – 2.5 between mRNA-1273 vs. mRNA-1273.222 vaccination during Month 6.5 and 18 in the post-Month 6 stage.

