These calculations are carried out assuming 5% annual dropout, 5% probability of missing any of the 3 doses, VE(COVID) of 63% between Month 0 and Month 6 in Group 1 (SARs-CoV-2 negative) and in Group 2, and 5% six-month COVID-19 incidence rate among unvaccinated PLWH SARs-CoV-2 negative individuals in the community. The assumption on VE(COVID) of 63% between Month 0 and Month 6 accounts for a possible reduced protection of the vaccine regimen in PLWH against the SARS-CoV-2 variant at the time of the trial conduct. The 5% six-month background incidence rate assumption was based on the observed 4.7%, 5.25%, and 10.38% placebo arm six-month incidence rates among baseline SARS-CoV-2 negative participants in, respectively, the AstraZeneca phase 3 (149), Novavax phase 2 (107), and Janssen ENSEMBLE phase 3 (28) trials restricted to South African study sites, and building in conservative margin given the availability of vaccines to potentially reduce transmission and infection in the region. The background SARS-CoV-2 (re-infection) incidence rate among unvaccinated PLWH SARS-CoV-2 positive individuals in the community is assumed to be half of that of unvaccinated PLWH SARS-CoV-2 negative individuals based on the reported protection of approximately 55% against the Omicron variant from previous SARS-CoV-2 infection in South Africa (150-152) and in other countries (153). The statistical power is calculated using an exact binomial test with a (two-sided) false positive error rate of 0.05.

**Table 6-2 Pre-Month 6 stage:** power to detect relative risk (Months 0-6) being different from 1.0 between Group 1 (n=4200) and Group 2 (n=8400).

True VE (0-6) of Group 1 (n=4200)	Relative Risk (Groups 1 vs. 2)	Total expected number of events M0-6	Power
60%	1.3	189	45%
	1.6	176	85%
	2.0	167	99%
70%	1.2	149	17%
	1.5	135	59%
	2.0	125	96%
70%	1/1.3	207	45%
75%	1/1.6	203	85%
80%	1/2.0	200	99%
75%	1/1.2	159	17%
80%	1/1.5	153	59%
85%	1/2.0	150	96%

**Post-Month 6 stage:** power to detect relative risk (Months 6.5-18) being different from 1.0 between mRNA-1273 vs. mRNA-1273.222 Month 6 vaccination (n=4000, 2000 vs. 2000),.

Annual incidence for mRNA-1273 Month 6 vaccination arm	Relative Risk (mRNA-1273 vs. mRNA-1273.222)	Total expected number of events M6.5-18	Power
3.5%	1.5	110	54%
	2.0	106	93%
3.0%	2.0	91	87%
	2.5	90	99%
2.5%	2.0	76	78%
	2.5	75	96%

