The relative risk (of COVID-19, severe COVID-19, SARS-CoV-2 infection, or SARS-CoV-2 asymptomatic infection) is defined as the incidence rate ratio between the 2 treatment groups in the pre-Month 6 stage or between the 2 treatment arms within a group in the post-Month 6 stage. When there are at least 7 severe COVID-19 endpoints at the primary analysis for a given relative risk assessment, both COVID-19 and severe COVID-19 are used as coprimary endpoints. Otherwise, severe COVID-19 is considered as a secondary endpoint. For the final analyses of the pre-Month 6 objectives, the incidence will be compared across groups by estimating the marginalized cumulative incidence of the endpoint overtime for each group, using a causal inference method that adjusts for potential confounders and accounts for right-censoring of failure times. Under causal assumptions, the marginalized cumulative incidence equals the causal cumulative incidence, interpreted as cumulative incidence if, hypothetically, the entire study population were assigned to the given group under consideration. Sensitivity analyses may also be conducted to account for unobserved confounding factors. For the final analyses of the post-Month 6 objectives, the RR between treatment arms within each group will also be estimated. The causal inference approach used for the pre-Month 6 stage analysis may also be applied for estimating the relative risk of each endpoint for the post-Month 6 dose objectives. More details will be described in the SAP. For analyses before the final analyses, the RR may be estimated from a Poisson regression analysis for both pre- and post-Month 6 stages. To assess potential time effects of vaccine efficacy, the Nelson-Aalen method will be used to plot the estimated cumulative incidence rates over time for the comparison groups. Additional analysis of RR by specified viral

strain categories may also be performed using competing risks failure time methods, as detailed in the SAP.

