For both the Cox regression approach and the cumulative incidence approach, if there are fewer than 20 COVE-/CDC-based COVID-19 endpoints, then the corresponding endpoint will only be studied descriptively. In a pre-specified Cox regression analysis, if the number of endpoints is fewer than the number of covariates to be adjusted multiplied by 5, then this analysis will only be conducted descriptively. Only studied descriptively means that numbers of endpoints by treatment arm and covariate strata are reported, but no estimation or testing of treatment effect parameters is performed.

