10.2 Selection of the final time point t_0

For analyses using study enrolment as the time origin, and for a given group comparison, the fixed time point t_0 is chosen to be minimum of 365 (or 540) days and the latest possible time point when stable estimation using follow-up data through the Month 12 (or Month 18) visit can be reasonably assured. For analyses using 13 days after the Month 6 vaccination as the time origin, and for a given group comparison, the fixed time point t_0 is chosen to be minimum of 165 (or 365) days and the latest possible time point when stable estimation using follow-up data through the Month 12 or Month 18 study visit can be reasonably assured. Identifying the minimum t_0 for which stable estimation can be assured is operationalized by selecting the latest point for which the standard error for the log risk ratio satisfies

$$\left| \frac{\log(3)}{\widehat{SE}(t)} \right| \geq z^{1-\alpha/2},$$

where $\widehat{SE}(t)$ denotes the estimated standard error for the log of the cumulative risk ratio at time t and $z^{1-\alpha/2}$ is the $1 - \alpha/2$ quantile of the standard normal distribution. The rationale is we would only consider an estimate valuable if we have enough precision to conclude that a large cumulative risk ratio (of size 3.0 or larger) is statistically significant at the level α . Study participants with an endpoint observed after t_0 are considered to have censored outcomes.

It is expected that, for analyses using the severe COVID-19 endpoint, the standard error may be very large for all time points due to a low event rate. Therefore, for analyses using study enrolment as the time origin, the time point t_0 is fixed at 365 (or 540) days for analyses through Month 12 (or Month 18), and for analyses using 13 days after the Month 6 vaccination as the time origin, t_0 is chosen to be 165 (or 365) days for analyses through Month 12 (or Month 18). That is, no data-adaptive selection of t_0 is performed when using the severe COVID-19 endpoint.

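### The protocol calls the study feasible to power for severe COVID-19, but its interim count suggests only about 5 to 7 severe events after Month 6, and power for a relative risk of 2 at the 7-event trigger is about 6% (equal arms, exact test)

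*Protocol*

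**What the plan says.** Protocol 2.1.1 gives three reasons for the co-primary status of severe COVID-19: its clinical importance; feasibility ("it is feasible to power the study for this endpoint given data showing that a sizable percentage of symptomatic infections are severe in trial countries"); a possible gain in power from using co-primary endpoints.

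Protocol 2.1, under the heading on modifying the final phase, describes serious COVID-19 before Month 6 as very rare, "with only 9 cases identified to date, including 7 in PLWH and 2 in people who were HIV-negative".

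Co-primary status is conditional. Protocol 6.1 acknowledges that the severe rate is uncertain and lets a treatment-blinded count decide. Section 6.4.3 sets the rule: "When there are at least 7 severe COVID-19 endpoints at the primary analysis for a given relative risk assessment", both endpoints are co-primary; otherwise severe COVID-19 is secondary. SAP 7.1 and 8.1 use the same number for the comparison of Month 6 vaccines.

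Protocol 6.3.1 limits its power calculations to symptomatic COVID-19, because the severe endpoint might be demoted. Neither document gives a power for severe COVID-19 or a reason for the number 7.

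For symptomatic COVID-19, SAP 7.1 says that "if there are fewer than 20 COVE-/CDC-based COVID-19 endpoints, then the corresponding endpoint will only be studied descriptively". SAP 10.2, on choosing the final time point, says "we would only consider an estimate valuable if we have enough precision" to find a cumulative risk ratio of 3.0 significant. It then uses a fixed time point for severe disease, where that criterion is not applied.

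**The concern.** The feasibility reason and the interim data sit in the same protocol and do not fit together. Section 2.1.1 is listed in the version history among the sections revised for version 8.0, yet the reason remains.

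The 7-event rule guards against a near-empty endpoint, but nothing shows that 7 events carry useful information. If the count reaches 7 or slightly more, severe disease stays a primary comparison with very little power. A non-significant result could then be read as showing that the vaccines, or the immunity groups, do not differ on the outcome that matters most clinically.

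**Working it through.** **Inputs from the documents**
- Method (protocol 6.3.1): "The statistical power is calculated using an exact binomial test with a (two-sided) false positive error rate of 0.05".
- Post-Month 6 setting (6.3.1): "approximately 4000 participants in Groups 1-4 received their Month 6 vaccination"; the table is for "power to detect relative risk (Months 6.5-18) being different from 1.0 between mRNA-1273 vs. mRNA-1273.222 Month 6 vaccination (n=4000, 2000 vs. 2000". Dropout is 5% a year.
- Interim count (2.1): 9 serious cases, 7 of them in PLWH. The 1298 participants with a positive NAAT were 9.3% of the total, so the denominator is 1298/0.093 = 13,957.
- Trigger (6.4.3; SAP 7.1 and 8.1): 7 severe events.

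**1. Reproducing the plan's own power.** Given D events in equal arms, the null share in one arm is 1/2 and the alternative is RR/(1+RR). The exact two-sided test reproduces all six post-Month 6 rows of Table 6-2:

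| Events | RR | Computed | Stated |
|---|---|---|---|
| 110 | 1.5 | 54.1% | 54% |
| 106 | 2.0 | 92.9% | 93% |
| 91 | 2.0 | 87.4% | 87% |
| 90 | 2.5 | 98.7% | 99% |
| 76 | 2.0 | 78.1% | 78% |
| 75 | 2.5 | 96.2% | 96% |

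**2. Severe events to expect after Month 6.** Follow-up per person at the interim is not stated, so 4 to 6 months is assumed, and serious is taken as severe. Post-Month 6 person-years: 4000 × 11.5/12 × (1 − 0.05 × 11.5/24) = 3,741.

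| Assumed interim follow-up | Rate per 100 person-years | Expected events | Poisson chance of 7 or more |
|---|---|---|---|
| 6 months | 9/(13,957 × 0.5) = 0.129 | 4.8 | 21% |
| 5 months | 0.155 | 5.8 | 36% |
| 4 months | 0.193 | 7.2 | 59% |

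The 95% Poisson interval on 9 cases is 4.1 to 17.1, which turns 4.8 into 2.2 to 9.2. As a cross-check, 86% of pre-Month 6 cases were asymptomatic, leaving 1298 × 0.14 = 182 symptomatic; 9/182 is about 5%. Applied to the 75 to 110 events of Table 6-2, that gives 3.7 to 5.4.

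**3. Power at exactly 7 events, equal arms.** A 7-0 split has p = 2 × (1/2)^7 = 0.016, and 6-1 has p = 2 × 8/128 = 0.125, so only 7-0 or 0-7 rejects.
- RR 2.0: (2/3)^7 + (1/3)^7 = 129/2187 = 5.9%.
- RR 3.0: (3/4)^7 + (1/4)^7 = 2188/16384 = 13.4%.
- For RR 2.0, 80% power is first reached at 72 events and sustained from 77.

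SAP 11.2 specifies a partial likelihood ratio test. With equal risk sets, a 6-1 split gives 2 × [6 ln(6/3.5) + ln(1/3.5)] = 3.96 > 3.84 and so rejects. Power at RR 2.0 is then 591/2187 = 27%, with a true type I error of 16/128 = 12.5%.

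**4. Power at 7 events, 1:2 groups (objective 2).** The null share in Group 1 is 1/3; at RR 2.0 it is 2/(2+2) = 1/2.
- Doubled-tail p-value: rejects at 6 or 7 of 7; power 8/128 = 6%.
- Minimum-likelihood p-value: 5 of 7 has p = 99/2187 = 0.045 and also rejects; power 29/128 = 23%.

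Table 6-2 cannot show which version was used, because the two give nearly the same power at its event totals.

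**5. Precision at 7 events.** SAP 10.2 requires log(3)/SE ≥ 1.96, so SE ≤ 0.56. For rare events the SE of the log risk ratio is about √(1/d1 + 1/d0). The best case with 7 events is 4-3: √(1/4 + 1/3) = 0.76. The criterion can first be met at 13 events (7-6: 0.556; 12 events at 6-6 give 0.577). A 4-3 split has an exact 95% interval for the relative risk of 0.23 to 9.1.

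**The case against.** **Status is conditional.** A reader might infer that the protocol keeps severe COVID-19 co-primary whatever the data show. It does not: at about 5 events after Month 6 its own rule makes the endpoint secondary. This stands. What remains is the case where the count reaches 7 or slightly more.

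**Feasibility is not a power claim.** Section 2.1.1 offers it as one of three reasons and cites data from the trial countries. No power is stated that could be called false. This also stands; the fault is an outdated reason with no figure behind it. The other two reasons are untouched.

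**The projection is not the protocol's.** It rests on assumed follow-up, on serious meaning severe, and on 9 cases. This is why it is given as a range.

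**Objective 2 is not hopeless.** A reader might infer that 7 cases in PLWH mean it cannot answer its question. The documents do not support that. At RR 2.0 power is 6% or 23% by the choice of exact p-value. The interim symptomatic rates in PLWH, 7.1% against 2.2%, give a ratio of about 3.2; if that held for severe disease, power would be 18% to 45%. That is low, not nil.

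**The SAP's other thresholds serve other purposes.** The 20-event rule covers a model with eight strata and covariates; severe disease is analysed without either. The 10.2 criterion selects a time point and does not decide whether an analysis is done. So neither shows that 7 breaks an existing rule, though 10.2 is still a fair yardstick for precision.

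**The label matters little.** There is no multiplicity adjustment, SAP section 7 says the study is not meant to license a product, and a wide interval would be visible. This limits the harm but does not support the feasibility reason.

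**Conclusion.** The concern holds in a limited form. The feasibility reason in 2.1.1 conflicts with the interim data in 2.1, no power for severe COVID-19 is given, and the 7-event trigger has no stated basis. About 5 to 7 severe events after Month 6 is a reasonable extrapolation if serious equals severe, the rate persists, and interim follow-up averaged 4 to 6 months. At 7 events, power for RR 2.0 is 5.9% in equal arms by the protocol's method, 6% to 23% at 1:2, and about 27% in equal arms by the SAP's test with an inflated error rate. All are far below 80%.

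For objective 2, the 7 PLWH cases would just meet the trigger if all are severe endpoints in the compared groups and counting window. The documents do not say so, and the count was interim.

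A reader might also infer that the trigger must rise to 20. That does not follow. Exact power for RR 2.0 in equal arms is 14% at 13 events and 30% at 20, so neither is a power-based value. For objective 2, raising the trigger after a count of 7 has been reported would be a demotion made with knowledge of the data.

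**What to change.** 1. **Protocol 2.1.1:** replace the second reason with a statement that, on interim data, the study is not powered for severe COVID-19. The first and third reasons can stay.
2. **Protocol 6.3.1:** give the power at 7 events (5.9% at RR 2.0 and 13.4% at RR 3.0 in equal arms; 6% to 23% at RR 2.0 for 1:2, naming the p-value used).
3. **Protocol 6.4.3 and SAP 7.1 and 8.1:** state that when the trigger is met with few events, severe COVID-19 is reported as counts by arm with an exact confidence interval, and that a non-significant result is not evidence of no difference. Put a number on few; 12 or fewer, the counts that cannot meet the SAP 10.2 criterion, is one available choice. An exact interval also remains usable at a 7-0 split, where the Cox estimate is infinite.
4. **Optional, post-Month 6 stage only:** a higher trigger, for example about 13 events from the 10.2 criterion, set blinded to arm.

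The cost is wording in three protocol sections and two SAP sections, with no new data. Item 4, if adopted, makes it more likely that severe COVID-19 becomes secondary after Month 6.

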## 2.1.2 **Background on the evolution of SARS-CoV-2 variants**

Since it was first recognized as a global threat in late 2019, the SARS-CoV-2 virus has adapted to immunologic selection pressures mediated by antibodies that limit, but do not necessarily eliminate, viral replication. Even before the availability of vaccines against SARS-CoV-2, new virus variants had begun to emerge worldwide and are thought to have significantly contributed to new waves of infections and deaths (60, 61). Mutations that lead to increased transmissibility and immunologic escape seem to most determine the success of new variants (38-40) (62-65).

Vaccine efficacy against VOCs can be compromised by alterations in the shape of the S protein, which can impair or inactivate binding sites for neutralizing antibodies (66-70).

The first major evidence of SARS-CoV-2 evolutionary change in response to selective pressure was the D614G mutation in the spike protein that emerged in early 2020 and has since become ubiquitous, likely because of its association with increased infectivity (71, 72). By the second half of 2020 the world entered a new stage of the pandemic characterized by the emergence of new SARS-CoV-2 variants with accumulations of mutations facilitating transmission despite population immunity while maintaining or even increasing viral replication (73). In September 2020 the United Kingdom first reported a new variant, B.1.1.7 (Alpha), which had D614G as well as several other important mutations that lent to increased transmission (74-76). By early 2021 Alpha had become the dominant variant in most of Europe, North America, and many parts of Asia and Africa (77). Soon after Alpha was identified, additional highly transmissible variants emerged in populations with significant immunity from prior infection, B.1.351 (Beta) in South Africa and P.1 (Gamma) in Brazil (78, 79). In addition to both strains being more transmissible, convalescent plasma or vaccine sera showed substantial reductions in neutralizing antibody titers compared to Alpha (80, 81). Both variants became dominant within their immediate region and some other countries, but both were displaced virtually entirely – along with most other variants worldwide – by the emergence of B.1.617.2 (Delta). First detected in India in December 2020, Delta had a number of previously detected and novel mutations which increased transmissibility, immune escape, and severity of disease (67, 82, 83) and led to an increase in cases and deaths in much world (84-86).

The emergence of B.1.1.529 (Omicron), first identified in Botswana and South Africa in November 2021, led to a massive global wave of infections and COVID-19 disease that dwarfed all previous surges (87). Genetically, Omicron had significantly more mutations than had been previously seen in variants, including over 30 in the S gene alone (88). Some of the mutations were ones seen in prior variants that were known to be associated with increased transmissibility, higher viral binding affinity, and immunologic escape (89, 90). But many of the mutations were novel. Phenotypically, the Omicron variant distinguished itself by its remarkable transmissibility, over three-fold greater than Delta, and by its ability to quickly spread in populations with prior immunity. Indeed, studies of the plasma neutralization of the Omicron variant demonstrated an unprecedented degree of neutralizing antibody escape (91, 92).

A leading hypothesis for the origin of Omicron is that it evolved during a chronic infection in someone immunocompromised (93). Indeed, an increasing number of studies suggest that prolonged infections in immunocompromised individuals, including PLWH, may be a major source of the multistep mutational changes associated with VOCs (44-46). In one study, researchers in South Africa examined a SARS-CoV-2 infection persisting over 6 months in a person with advanced HIV that started as ancestral virus but evolved various mutations found in Omicron and

[figure not shown]
other variants and developed substantial immune escape from mRNA-1273 vaccine-associated immunity (45). These findings highlight the urgent need for a better understanding mutational evolution within PLWH of different degrees of immunosuppression to help inform strategies to prevent emergence of further VOCs.

